### 2.4 Safety objective(s)

1. To evaluate the effect of BGS649 after 12 months period of treatment with active study drug (6 months treatment in Study MBGS205 and 6 months treatment in Study MBGS206) by dose group on:
  - o Bone turnover biomarkers
  - o Bone mineral density and bone biomarkers by vitamin D status (Baseline vitamin D from Study MBGS205)
  - o Oestradiol levels
  - o Testosterone outside upper limit of normal range
  - o Prostate specific antigen and haematocrit
  - o Blood Pressure
  - o Adverse events (AEs)
2. To evaluate any association between changes in bone mineral density after 12 months treatment with BGS649 with end of treatment testosterone and oestradiol levels
3. To collect safety data in subjects switching from placebo arm in Study MBGS205 and treated with 6 months active study drug in Study MBGS206

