### 4.2 Secondary Endpoints

#### 4.2.1 Secondary Safety Endpoints

1. In subjects that were randomized to active treatment in Study MBGS205 by dose group:
  - o Percentage change in hip (total and femoral neck) bone mineral density measured by DEXA (g/cm^2) from Baseline in Study MBGS205 to Week 48 in Study MBGS206
  - o Percentage change in bone turnover markers (C-terminal telopeptide [CTx1], osteocalcin, bone alkaline phosphatase, and procollagen type 1 N-propeptide [P1NP]) from Baseline in Study MBGS205 to Week 48 in Study MBGS206
  - o Proportion of subjects with T-scores  $\leq$  -2.5 at Week 48
  - o Percentage change in bone density and bone biomarkers adjusted for vitamin D deficiency from Baseline in Study MBGS205 to Week 48 in Study MBGS206
  - o Change of oestradiol (absolute and percentage) from Baseline in Study MBGS205 to Week 48
  - o Proportion of subjects that overshoot testosterone (total testosterone above 1000 ng/dl [35 nmol/L], from first dose of study drug in Study MBGS205 until study completion)
  - o Change in PSA from Baseline in Study MBGS205 to Week 48 in Study MBGS206
  - o Change in haematocrit from Baseline in Study MBGS205 to Week 48 in Study MBGS206
  - o Change in blood pressure (systolic and diastolic) Baseline in Study MBGS205 to Week 48 in Study MBGS206
  - o Treatment emerged AE, SAE, and AESI (from first dose of study drug in Study MBGS205 until study completion)
  - o Relationship between change in bone mineral density from Baseline in Study MBGS205 to Week 48 in Study MBGS206 and absolute levels of oestradiol and total testosterone at Week 48 in MBGS206

2. In subjects that were randomized to placebo in Study MBGS205 by dose group:
  - o Percentage change in lumbar bone mineral density measured by DEXA (g/cm^2) from Baseline in Study MBGS206 to Week 48
  - o Percentage change in hip (total and femoral neck) bone mineral density measured by DEXA (g/cm^2) from Baseline in Study MBGS206 to Week 48
  - o Percentage change in bone turnover markers (CTx1, osteocalcin, bone alkaline phosphatase, and P1NP) from Baseline in Study MBGS206 to Week 48
  - o Change of oestradiol (absolute and percentage) from Baseline in Study MBGS206 to Week 48
  - o Proportion of subjects with T-scores  $\leq -2.5$  at Week 48 of Study MBGS206

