#### 8.6.1 Analysis methods

For binary outcomes the proportion of subjects with a response will be summarised and compared between treatment regimens using Fisher's Exact Test.

For continuous parameters, the change from baseline will be summarised by treatment arm and visit. A single sample 2-sided t-test conducted at the 5% significance level will be used to analyse the change from baseline to Week 48 within each treatment arm. In addition, the change from baseline will be assessed with a mixed model repeated measure (MMRM) analysis. Analyses will include the fixed, categorical effects of treatment, visit, and treatment-by-visit interaction, as well as the continuous, fixed covariates of the associated baseline value and baseline-by-visit interaction. An unstructured covariance matrix will be used to model the within-subject errors. If the model with the unstructured covariance matrix fails to converge, other covariance structures, including Toeplitz, compound symmetry, and spatial power, will be considered. The denominator degrees of freedom will be calculated according to the Kenward-Roger method. Significance tests for treatment differences will be based on least-squares means.

Associations between changes in PROs and changes in body composition, physical activity, sleep, and grip strength will be assessed with correlation coefficients and with separate linear regression models in which changes in PRO measure total or subscale scores will be taken as the predictor variable, and baseline score as a covariate. The associations between changes in testosterone and changes in PROs, body composition, physical activity, grip strength, and sleep will be assessed in the same way. Correlation coefficients, Beta coefficients, standard errors, and 95% CIs will be presented.

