### **8.7.1 DXA Scans**

DXA Scan assessments will only be performed at the EOT visit (for subjects that reached at least Week 36) and will be over-read by IMI. Both the site assessed and the over-read data will be used for all statistical analysis and utilise the visit windows specified in Appendix F. If multiple assessments are recorded within the window, the closest to the target date will be used for analysis.

Descriptive statistics (observed values, changes from baseline and percentage change from baseline) in hip (total and femoral neck) bone density will be presented. In addition descriptive statistics (observed values and changes from baseline) for the associated T-scores in both the lumbar spine and hip will be presented for each treatment regimen and time-point.

A shift table of baseline severity categories (Normal, Osteopenia and Osteoporosis) to post baseline severities will be generated by treatment regimen and visit.

Change from baseline in bone density (in both the lumbar spine and hip) to Week 48 for subject randomised to active treatment in Study MBGS205 will be analysed via MMRM in the same manner as the change from baseline in total testosterone (see Section 8.6.3.3).

Change from baseline in bone density (in both the lumbar spine and hip) to Week 48 for subjects randomised to placebo in Study MBGS205 will be analysed using an ANCOVA model with treatment as a fixed effect and the associated baseline value as a covariate. Least squares means and standard errors will be presented for each visit, p-value and 2-sided 95% confidence interval for treatment differences across all doses will be presented for each visit. Significance tests will be based on least-squares means using a two-sided  $\alpha = .05$ .

In addition subgroup descriptive summary tables of change in bone density by subjects with and without 25 hydroxy vitamin D deficiency at baseline (vitamin D deficiency is defined as 25 hydroxy vitamin D < 30ng/ml) will be presented.

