### 8.7.2 Bone turnover markers

Descriptive summary tables will be presented for all bone turnover marker (C-terminal telopeptide [CTx1] and procollagen type 1 N-propeptide [P1NP], osteocalcin and bone alkaline phosphatase) values, change from baseline and percentage change from baseline by treatment regimen and visit.

The change from baseline and percentage change from baseline in each parameter up to Week 48 will be analysed via MMRM in the same manner as the change from baseline in total testosterone (see Section 8.6.3.3). Analyses will be conducted separately for subjects that were randomised to active treatment and subjects that were randomised to placebo treatment in study MBGS205.

Line graphs of absolute bone turnover marker parameters will be provided by treatment regimen and boxplots of observed values by treatment and visit will be generated for all bone turnover markers.

In addition subgroup descriptive summary and analysis tables of bone turnover markers by subjects with and without 25 hydroxy vitamin D deficiency at baseline (vitamin D deficiency is defined as 25 hydroxy vitamin D < 30ng/ml) will be presented.

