### 9 CHANGES TO PLANNED ANALYSIS FROM STUDY PROTOCOL

The below are changes to the study protocol analysis:

The Percentage change in lumbar bone mineral density measured by DEXA (g/cm^2) from Baseline in Study MBGS206 to Week 48 for subjects that were randomised to placebo in Study MBGS205 has been added as a secondary safety endpoint. This was inadvertently absent from the study protocol.

Vitamin D deficiency is defined in the protocol as <20ng/ml. For all analyses Vitamin D deficiency has been defined as <30ng/ml.

Following data integrity concerns at site 1156, sensitivity analyses were added to assess the impact of the site on key parameters.

---

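### No planned model produces the vitamin D-adjusted change in bone density and bone markers that both documents list as a secondary safety endpoint

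*SAP*

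**What the plan says.** **Endpoint.** SAP 4.2.1 lists, for men randomised to active treatment in MBGS205 and by dose group: "Percentage change in bone density and bone biomarkers adjusted for vitamin D deficiency from Baseline in Study MBGS205 to Week 48 in Study MBGS206". Protocol 13.4.2.1 and the synopsis carry the same item. It is not listed for the men who switched from placebo.

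**Objective.** The matching safety objective (protocol 8.2.1, SAP 2.4) is worded differently: "Bone mineral density and bone biomarkers by vitamin D status (Baseline vitamin D from Study MBGS205").

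**Analysis of BMD.** For active-randomised men, SAP 8.7.1 states that change in lumbar and hip density "will be analysed via MMRM in the same manner as the change from baseline in total testosterone (see Section 8.6.3.3"). That section relies on the general model in 8.6.1: "Analyses will include the fixed, categorical effects of treatment, visit, and treatment-by-visit interaction", with baseline value and baseline-by-visit as the only covariates. The only vitamin D output for BMD is this: "In addition subgroup descriptive summary tables of change in bone density by subjects with and without 25 hydroxy vitamin D deficiency at baseline".

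**Analysis of bone markers.** SAP 8.7.2 uses the same type of model for change and percentage change, and then adds: "In addition subgroup descriptive summary and analysis tables of bone turnover markers by subjects with and without 25 hydroxy vitamin D deficiency at baseline".

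**Declared changes.** SAP section 9 lists the departures from the protocol. Removing a vitamin D adjustment is not among them.

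**The concern.** An endpoint described as adjusted for a baseline factor calls for one estimate per dose group in which that factor has been accounted for. Splitting men into deficient and non-deficient and describing each half does not give that. It yields two sets of summaries per dose and leaves the reader to combine them.

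The endpoint also concerns the trial's main safety question, bone loss under an aromatase inhibitor. If the plan is carried out to the letter, the study report will have nothing to put against this listed item. Any adjusted analysis would then have to be devised after the data are known, with free choice of model, scale and coding of vitamin D.

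**Working it through.** No figure in the documents bears on this point, so the check sets the endpoint against every analysis that could deliver it.

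| Where | Outcome | Terms or method | Vitamin D term |
|---|---|---|---|
| Protocol 13.5.3.1 | Percentage change, BMD and markers | Summaries by arm and visit, 95% CI for mean change; one-sample t-test for hip; detail left to the SAP | None |
| SAP 8.6.2 | Percentage change, lumbar BMD | One-sample t-test in each arm | None |
| SAP 8.7.1, active-randomised men | Change, lumbar and hip BMD | MMRM: treatment, visit, treatment-by-visit, baseline, baseline-by-visit (from 8.6.1) | None |
| SAP 8.7.1, placebo-switch men | Change, lumbar and hip BMD | ANCOVA: treatment, baseline | None |
| SAP 8.7.1, last paragraph | Change, BMD | Descriptive tables split by deficiency | Stratifier only |
| SAP 8.7.2 | Change and percentage change, markers | MMRM as above | None |
| SAP 8.7.2, last paragraph | Markers | Descriptive and analysis tables split by deficiency | Stratifier only |
| SAP 8.8.3 and 8.8.4 | Associations; sensitivity analysis for one site | Vitamin D not mentioned | None |

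Four things follow.

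1. **No adjusted estimate exists for BMD.** Vitamin D enters only as a way of splitting descriptive tables. Under SAP 8.1.3, descriptive statistics are counts, mean, median, SD and range; nothing there combines the two strata.
2. **No adjusted estimate exists for the markers.** Their subgroup tables include analysis as well as description, but still within each stratum. BMD therefore gets less than the other half of the same endpoint, and neither half gets the adjustment.
3. **The scale differs for BMD.** The endpoint is percentage change. The 8.7.1 model and its subgroup tables are worded as change, although the total testosterone section to which the model refers uses percentage change. For the markers, 8.7.2 already models percentage change.
4. **The data are available.** SAP 8.4.2 summarises vitamin D among the baseline characteristics, and the objective names the MBGS205 baseline value.

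**Cost in parameters.** A two-level deficiency status uses 1 degree of freedom. Appendix F gives active-randomised men two post-baseline DEXA visits (Weeks 24 and 48), so a status-by-visit term adds 2 − 1 = 1, for a total of 2. For the markers, the schedule shows Weeks 24, 36 and 48, so the total is 1 + (3 − 1) = 3, or more if other MBGS205 visits enter the model. The target is about 25 completers in each of three dose groups, or 3 × 25 = 75 men.

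**The case against.** The best defence is that the subgroup tables are what the trial meant. The objective speaks of results by vitamin D status, and tables with and without deficiency answer that. The protocol's own analysis section never described a vitamin D model either. On this view the endpoint wording is loose and nothing is missing. That stands in part: the objective is served, and the documents disagree with themselves between objective and endpoint. It does not supply the adjusted estimate that both endpoint lists call for, and section 9 does not resolve the conflict.

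A second defence is that the consequence is small: every analysis is labelled exploratory, and this is one of many secondary safety endpoints. That stands in full and limits the weight of the point.

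A reader might go further and infer that dose differences in BMD are confounded by vitamin D. The documents do not support this. The dose groups come from the MBGS205 randomisation. Only completers who were eligible and consented carry on, but nothing in the documents links that selection to vitamin D. Chance imbalance between randomised arms is part of the sampling error that the confidence interval already reflects. A reader might also want to attach a precision figure to the subgroup cells. The only SD shown is 0.0439 g/cm² (protocol 13.1). Turning it into a percentage needs a mean baseline BMD, and sizing the cells needs a deficiency prevalence; the documents give neither.

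**Conclusion.** The concern holds as a mismatch between endpoint and analysis. One listed secondary safety endpoint has no corresponding estimate, for BMD at spine and hip and for all four bone markers, and the omission is not declared. This rests on the text alone and needs no numerical assumption. No size of bias is claimed, because the documents give neither the prevalence of deficiency nor its relation to BMD change.

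It should not be read as a threat to the primary result. That is a one-sample test within each arm against a 3% decrease, so vitamin D balance between doses does not enter it. Nor does it call for a change to the placebo-switch ANCOVA, since the endpoint is not listed for those men. It is worth correcting because the correction is cheap and the plan otherwise does not deliver what it lists.

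**What to change.** For men randomised to active treatment in MBGS205:

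- Fit the 8.7.1 BMD model on percentage change, and the 8.7.2 marker models on percentage change, with baseline MBGS205 vitamin D deficiency status (as the SAP defines it) added as a covariate. Include a status-by-visit term if it is to match the existing baseline-by-visit term.
- Report the adjusted mean percentage change at Week 48 with a 95% CI for each dose. State the mix of deficient and non-deficient men at which the means are evaluated.
- Optionally, repeat with continuous 25-hydroxy vitamin D as a sensitivity analysis.
- Keep the subgroup tables as descriptive output for the by-status objective.
- Record the clarification in SAP section 9, so that objective, endpoint and analysis agree.

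The cost is one or a few degrees of freedom in models already planned, with no new data. If the sponsor wants only a description by status, the minimum is to reword the endpoint accordingly and log that in section 9; this removes the inconsistency but gives up the adjusted estimate.

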### 8.7.2 Bone turnover markers

Descriptive summary tables will be presented for all bone turnover marker (C-terminal telopeptide [CTx1] and procollagen type 1 N-propeptide [P1NP], osteocalcin and bone alkaline phosphatase) values, change from baseline and percentage change from baseline by treatment regimen and visit.

The change from baseline and percentage change from baseline in each parameter up to Week 48 will be analysed via MMRM in the same manner as the change from baseline in total testosterone (see Section 8.6.3.3). Analyses will be conducted separately for subjects that were randomised to active treatment and subjects that were randomised to placebo treatment in study MBGS205.

Line graphs of absolute bone turnover marker parameters will be provided by treatment regimen and boxplots of observed values by treatment and visit will be generated for all bone turnover markers.

In addition subgroup descriptive summary and analysis tables of bone turnover markers by subjects with and without 25 hydroxy vitamin D deficiency at baseline (vitamin D deficiency is defined as 25 hydroxy vitamin D < 30ng/ml) will be presented.

### 8.7.3 Oestradiol and testosterone/oestradiol ratio

Descriptive summary tables will be presented for oestradiol and testosterone/oestradiol ratio values, change from baseline values and percentage change from baseline values by treatment regimen and visit. High sensitivity Oestradiol values collected during MBGS205 will be summarised together with

the Oestradiol values assessed by the Central lab.

The change and percentage change from baseline in each parameter up to Week 48 will be analysed in the same manner as the change from baseline in bioavailable testosterone (see Section 8.6.3.5). Analyses will be conducted separately for subjects that were randomised to active treatment (MMRM analysis) and subjects that were randomised to placebo (ANCOVA analysis) in study MBGS205. A figure of absolute oestradiol will be provided by treatment regimen.

In addition the number and proportion of subjects with oestradiol values < 11 pg/mL will be summarised by treatment regimen at each visit.

### 8.7.4 Adverse events

All AEs will be classified by SOC and PT according to the MedDRA Version 19.1 or higher.

Details for imputing missing or partial start dates of adverse events are described in Section 7.2.2.4.

All AE summaries will be generated by active treatment period (across both MBGS205 and MBGS206), MBGS206 treatment period, MBGS206 follow-up period and overall (i.e including those that started in both the active treatment period and follow-up period).

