### 3.3 Study treatments and assessments

During the 24 week treatment period subjects in the BGS649 groups will take the required dose [REDACTED] Subjects will receive three capsules per dose to deliver a total of [REDACTED]

Dose changes are not permitted during the treatment period.

The maximum MBGS206 study duration from baseline to end of the safety follow-up period is 36 weeks which yields to a maximum duration across both MBGS205 and MBGS206 of 60 weeks.

A detailed description of procedures and assessments to be conducted during this study is summarised in the Schedule of Study Assessments in Table 1 below.

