### **7.1.4 Definitions relative to safety parameters**

#### **7.1.4.1 Adverse Event (AE)**

##### Treatment Emergent Adverse Event (TEAE)

A Treatment Emergent AE (TEAE) is defined as an AE occurring or worsening on or after the first dose of active study medication (from either MBGS205 or MBGS206).

TEAEs will also be split between AEs that start during the subject's active treatment period (for subjects randomised to active in MBGS205 this includes AE's starting in study MBGS205) and those that start on or after the first day of the MBGS206 follow-up period. A further category of TEAEs that started in MBGS206 but prior to the MBGS206 follow up period will also be utilised for summary tables (TEAEs started in MBGS205 would be excluded from this category).

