#### 8.1.2 Treatment groups

Statistics will be displayed for the following treatment regimens in the below order:

- BGS649 [REDACTED]
- BGS649 [REDACTED]
- BGS649 [REDACTED]
- Active Total (Includes all continuous active groups where applicable)
- Placebo -> BGS649 [REDACTED]
- Placebo -> BGS649 [REDACTED]
- Placebo -> BGS649 [REDACTED]
- Plabebo-> Active Total (Includes all Placebo-> Active Groups where applicable)
- Overall Total (Includes all groups where applicable)

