#### Notes:

- Two AEs with the same PT will be considered as two different events when calculating the “number of events” in the tables.
- Where a subject has the same AE, based on preferred terminology, reported multiple times in the same category the subject will only be counted once at the preferred terminology level in AE frequency tables.
- Where a subject has multiple AEs within the same SOC in the same category, the subject will only be counted once at the SOC level in AE frequency tables.
- AEs where the intensity is missing will be assumed to be “Severe”
- AEs where the causality is missing will be assumed to have “Reasonable possibility of relatedness”

An overall summary of AEs will be provided. The total number of events and number and proportion of subjects experiencing any AEs, TEAEs, TEAEs of special interest, AEs related to study medication (i.e where the investigator has recorded “Reasonable possibility of relatedness”), SAEs, SAEs related to study medication, severe AEs, AEs leading to permanent discontinuation of study treatment and AEs leading to death will be tabulated for each treatment regimen and overall.

Additionally, TEAEs, TEAEs of special interest, related TEAEs, serious TEAEs, related SAEs, AEs leading to permanent discontinuation of study treatment and AEs leading to death will be summarised by SOC and PT for each treatment regimen and overall (number and percentage of subjects experiencing at least one AE per PT as well as the number of observed events per PT). All TEAEs will also be summarised separately by maximum intensity for each SOC and PT and by causality for each SOC and PT.

A table presenting the number and percentage of subjects with at least one AE and the number of AEs for the most common treatment-emergent AEs (reported in  $\geq 1\%$  of patients in any treatment regimen) will be provided. PTs will be used for tabulation, sorted by decreasing overall frequency.

All AEs will be presented in full in a comprehensive listing including subject number, treatment regimen, intensity, seriousness, actions taken, outcome, causality, onset/stop and duration. Details of all TEAEs of special interest, SAEs, AEs leading to permanent discontinuation of study treatment and AEs leading to death will be listed separately.

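### The SAP's overall and active-treatment-period AE tables set windows of up to 60 and 48 weeks beside, and pooled with, windows of up to 36 and 24 weeks, with no person-time rate

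*SAP*

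**What the plan says.** SAP 7.1.4.1 starts the treatment-emergent window at first active drug: "A Treatment Emergent AE (TEAE) is defined as an AE occurring or worsening on or after the first dose of active study medication". For men randomised to BGS649 in MBGS205, that dose was in MBGS205. For men randomised to placebo there, it is the first MBGS206 dose. The endpoints in SAP 4.2.1 follow the same split. The entry for continuing men reads "Treatment emerged AE, SAE, and AESI (from first dose of study drug in Study MBGS205 until study completion", and the entry for switchers starts in MBGS206.

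SAP 3.3 gives the lengths: "The maximum MBGS206 study duration from baseline to end of the safety follow-up period is 36 weeks", and "a maximum duration across both MBGS205 and MBGS206 of 60 weeks".

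SAP 8.7.4 lists four sets of AE tables: "All AE summaries will be generated by active treatment period (across both MBGS205 and MBGS206), MBGS206 treatment period, MBGS206 follow-up period and overall". For the MBGS206 treatment-period set, SAP 7.1.4.1 adds that "TEAEs started in MBGS205 would be excluded from this category".

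The columns come from SAP 8.1.2: three continuing-dose groups and their total, three placebo-switch groups and their total, then "Overall Total (Includes all groups where applicable". The statistics by system organ class and preferred term are the "number and percentage of subjects experiencing at least one AE per PT as well as the number of observed events per PT". No person-time rate or time-to-event summary is planned for AEs, SAEs or AESIs.

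**The concern.** A crude percentage of men with an event depends on how long the men were observed. In two of the four table sets the observation time differs by design between the continuing and the switched columns, and the last column merges them. A reader who sets a dose beside its placebo-switch counterpart cannot separate a difference in risk from a difference in time. Raw event counts have the same weakness, because they too grow with time.

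Other planned output does not supply the missing denominator. Treatment duration (SAP 8.5.1) is tabulated on its own and is not linked to AE incidence. Follow-up time (SAP 7.1.1, summarised under 8.2) starts at the first MBGS206 dose for everyone. It would read about 36 weeks for continuing men whose overall AE window is up to 60. SAP 8.6, 8.7.2 and 8.7.3 analyse the two cohorts separately for efficacy, bone turnover markers and oestradiol; 8.7.4 has no such rule.

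AEs after 12 months on drug and safety in the switchers are both stated objectives (SAP 2.4). These tables are where a reader will look for them.

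**Working it through.** **Inputs.** 24 weeks of treatment in MBGS205, 24 weeks in MBGS206 and 12 weeks of follow-up (SAP 3.1); the TEAE start point (SAP 7.1.4.1); 30 continuing men planned per dose (protocol 13.1; SAP 3.1), so 90 for three doses. The documents give neither AE rates nor the number of switchers, so both are assumed below over a range.

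**Step 1: reproduce the plan's durations.** 24 + 12 = 36 weeks and 24 + 24 + 12 = 60 weeks. Both agree with SAP 3.3.

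**Step 2: planned maximum window per table set, in weeks.**

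| Table set | Continuing active | Placebo switchers | Ratio |
|---|---|---|---|
| Overall | 60 | 36 | 1.67 |
| Active treatment period | 48 | 24 | 2.00 |
| MBGS206 treatment period | 24 | 24 | 1.00 |
| MBGS206 follow-up | 12 | 12 | 1.00 |

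The third row is equal in calendar time but not in time on drug. Continuing men are in weeks 25-48 of BGS649 and switchers in weeks 1-24. No planned table shows the same weeks on drug for both cohorts.

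**Step 3: effect of window length alone.** Assume the same constant hazard in both cohorts. If p is the risk over the shorter window, the risk over the longer one is 1 - (1 - p)^(60/36) for the overall tables and 1 - (1 - p)^(48/24) for the active-period tables.

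| p in shorter window | Overall: 36 to 60 weeks | Active period: 24 to 48 weeks |
|---|---|---|
| 5% | 8.2% | 9.8% |
| 10% | 16.1% | 19.0% |
| 20% | 31.1% | 36.0% |
| 30% | 44.8% | 51.0% |
| 50% | 68.5% | 75.0% |

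For p from 10% to 30% the gap is 6.1 to 14.8 points in the overall tables and 9 to 21 points in the active-period tables, with no difference in risk.

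**Step 4: the pooled column.** Take a 36-week risk of 20%, 90 continuing men and m switchers. Overall Total = (90 × 0.3106 + m × 0.20)/(90 + m). This gives 29.5% for m = 15, 28.3% for m = 30 and 27.4% for m = 45. None of these is the 36-week risk (20%) or the 60-week risk (31.1%), and the value moves with the mix of cohorts.

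**Step 5: does a rate remove the artefact?** Full person-time per man is 60/52.18 = 1.15 years or 36/52.18 = 0.69 years. A 10% risk at 36 weeks is a hazard of -ln(0.90)/0.69 = 0.153 per year, or 15.3 first events per 100 patient-years. At 60 weeks, -ln(1 - 0.161)/1.15 gives the same 15.3. The two columns agree, as they should.

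**Step 6: where that rate would mislead.** Suppose an event would have barred a man from MBGS206, so that continuing men have almost none in their first 24 weeks. Counting those weeks multiplies their rate by about 24/48 = 0.50 in the active-period tables and 36/60 = 0.60 in the overall tables. Time for such events has to start at the first MBGS206 dose.

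**The case against.** A reader might infer that every AE and AESI table is distorted. The documents do not support that. The sentence in SAP 8.7.4 also plans the MBGS206 treatment-period and follow-up sets, which have equal planned windows, and the first of these excludes events that began in MBGS205.

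A reader might also infer that continuing men must show more events of every kind. That does not follow either. They entered only if they had finished 24 weeks with no MBGS205 discontinuation criterion met (protocol 9.3.1 and 9.3.2). Of the eight AESIs in protocol 12.1.7, six correspond to mandatory discontinuation criteria in protocol 9.3.4: cardiovascular event, prostate cancer, haematocrit above 54%, fragility fracture, sleep apnoea and breast cancer. A seventh, osteoporosis by DEXA, is largely screened out by the T-score exclusion. The MBGS205 criteria are not in these documents, so their similarity is an assumption, and a transient haematocrit alert could still be counted. For most AESIs, and for AEs leading to discontinuation, the direction of the net bias cannot be stated. This objection stands in full, and it shapes the fix.

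It can further be said that no AE comparison between cohorts is planned, AE output is descriptive, all analyses are exploratory (SAP 8.6.1.1), and the columns are labelled by cohort with separate subtotals. That limits the weight of the point. It does not give Overall Total a meaning.

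Finally, some information is recoverable. Continuing men's event counts for weeks 1-24 are the active-period count minus the MBGS206 treatment-period count, and all AEs are listed with onset dates. Subject percentages cannot be obtained by subtraction. The table templates are in a separate document, so the exact layout cannot be checked.

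**Conclusion.** The point holds for two of the four table sets and for their pooled column. The window ratios of 1.67 and 2.00 follow directly from the SAP. The 6 to 21 points are illustrative: they assume a constant hazard, equal in both cohorts, and risks of 10% to 30% in the shorter window. The 60-versus-36-week figures also apply one hazard to treated weeks and to the 12 weeks off drug. All windows are planned maxima, which early discontinuation shortens. The illustration suits general TEAEs and SAEs, and does not carry over to events that would have kept a man out of MBGS206.

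A reader might also infer that the dose comparison is biased. It is not, on this ground: within the continuing cohort, and within the switchers, every dose has the same planned window. Nor is the primary bone density analysis touched. This is a cheap improvement to the safety reporting.

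**What to change.** In SAP 8.7.4, for the overall and active-treatment-period sets only:

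- Add exposure-adjusted incidence for TEAEs and SAEs: subjects with a first event, and events, each per 100 patient-years from first active dose. End the person-time where the table's period ends.
- Drop the crude percentage from Overall Total, or replace it with the rate.
- For AEs leading to discontinuation, and for AESIs that would have barred entry to MBGS206, base the rate on time from the first MBGS206 dose. Say in a footnote that continuing men were selected for completing 24 weeks without a discontinuation criterion.
- If a table limited to the first 24 weeks on active drug is added, restrict it to general TEAEs and give it the same footnote.

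The protocol should also be reconciled on where the window starts. Section 12.1.1 starts TEAEs at the first MBGS206 dose, while 13.5.3.1 and the SAP start them at the first MBGS205 dose for continuing men.

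The cost is small. AE onset dates, study day from first active dose (SAP 7.1.1) and duration of active exposure (SAP 7.1.4.2) are already planned. One new variable is needed: follow-up time from first active dose. The output becomes slightly longer, and the rates carry the constant-rate and selection caveats.
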